5.2 Analysis of the secondary endpoints

Included subjects

All secondary outcomes assessed at follow-up visits (glycaemic control outcomes and PROMs) will be included in the analysis, similar to what is described for the primary outcome. The cost-effectiveness analysis is described separately in section 6.3.

5.3 Baseline descriptive statistics

Baseline characteristics of all included patients will be reported for each treatment (index and control) group separately, for both arms (see below). Continuous variables will be included as means with standard deviations, medians with 25th and 75th percentiles and number of non-missing values, categorical variables will be reported as numbers with percentages and number of non-missing

values. Patients, sex, age, center of inclusion as well as all other baseline measurements of primary and secondary outcomes (where applicable) will be included in the table. In line with current recommendations for clinical trials,¹⁷ p-values for a comparison between treatment and control groups at baseline will not be included.

Baseline variables:

- Age;
- Sex;
- Body mass index (kg/m²);
- Systolic and diastolic blood pressure (mmHg) and pulse (beats/min);
- HbA1c (mmol/mol);
- Duration of diabetes (years);
- Specification current treatment (sensor/pump and type);
- Duration of current treatment (years);
- Patient reported daily insulin use (units/day);
- Diabetes complications and treatment (yes/no):
- Retinopathy:
 - Retinopathy and treatment;
 - Maculopathy and treatment;
- Nephropathy:
 - eGFR (mL/min/1.73 m2);
 - Albuminuria (micro-/macroalbuminuria);
- Neuropathy:
 - Distal neuropathy;
 - Gastric autonomic neuropathy;
- Macro-angiopathy:
 - Cardiac;
 - o Cerebral;
 - Peripheral;
 - o Other;
- Non-diabetic disease;
- Smoking (yes/no);
- Alcohol (units/week);
- Education level;
- Professional status;
- Domestic situation.

6. Statistical methods

6.1 Primary endpoint

The primary endpoint (mean TIR at 12 months) will be compared between the DHFCL treatment and the two control treatments. The analysis will be performed for each of the study arms (see above) separately. To obtain this comparison, a mixed model analysis for continuous outcomes will be performed with TIR at 3, 6, 9 and 12 months (hence forward referred to as time) as dependent variable. This is a linear regression model that includes a random intercept for center of inclusion and a residual covariance matrix to correct for multiple measurements per patient. The initial analysis will be performed with a heterogeneous autoregressive matrix that assumes different variances for each measurement, a constant correlation between adjacent measurements and consistently lowering correlation when time between measurements is longer. The first analysis will include time, treatment and an interaction between time and treatment as fixed effects. In the second analysis, correction for the predefined prognostic factors, i.e. TIR at baseline, patients age and sex, will be included in the analysis as fixed effects. As the primary endpoint comparison is defined at 12 months, a specific contrast will be included in the analysis to compare mean TIR at 12 months between DHFCL control treatments. Results will be reported as difference in mean TIR with 95% confidence intervals (CIs). P-values will only be reported for the primary analysis in the ITT population. Study arm 1 and 2 will be considered two separate trials in different populations and as such no multiplicity correction is planned for performing these two primary comparisons under a single study protocol. The p-value for study arm 1 and study arm 2 will each be separately compared to the threshold 0.05 to declare significance.

The primary analysis may result in convergence problems when the residual covariance matrix is not correctly specified, given the data. In this case, the residual covariance matrix may be adjusted. Convergence problems may also arise for the estimation of the random intercept for center of inclusion when one or more centers include a low number of patients or when included patients from different centers show very similar outcome measurements. In this case, the random intercept may be excluded from the analysis and the addition of a variable representing academic centers versus peripheral centers may be added to the analyses models as a fixed effect. The regression model with residual covariance matrix is specifically chosen as the primary analysis, as it allows to incorporate all non-missing measurements of patients over time. Further details on missing outcomes are given in section 7 on missing data.

Validity of the distributional assumptions for the main analysis model (normal distribution, homoscedasticity) will be assessed with residual analysis. Raw residuals from a covariance pattern model may (compared to a 'standard' linear regression) show both correlation and unequal variances. Raw residuals will be transformed with Cholesky decomposition prior to the assessment described in this section.¹⁸

Histograms and QQ-plots will be created to assess normality of residuals. Residuals will be plotted against raw and normalized predicted values to assess homoscedasticity and linearity. Violation of the assumption of homoscedasticity will be corrected with robust (i.e. Hubert-White's) estimation of standard errors.¹⁸

When a serious violation of the normality assumption is observed in the residual plots, the main analysis will be changed to a mixed regression analysis based on beta distributions.¹⁹ The steps for inclusion of predefined prognostic factors will be included as specified for the primary analysis (see above). Multiple measurements per patient will be corrected with a random intercept. The residual covariance matrix will be excluded from the model, as such models cannot be estimated under maximum likelihood.

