3.1 Study arm 1: HCL as control treatment and DHFCL as index treatment

A recent cross over study of the index intervention treatment (DHFCL) showed a median mean TIR of 86% (SD 4%).¹ Previous studies show a mean TIR under HCL treatment of 70 to 78% (SD 16% to 17%). ²⁻⁴ To be conservative, we assume a 7% increase in mean TIR from 78% under the HCL control treatment (SD 17%) to 85% under the index intervention treatment (SD 4%), using the two sample t-test with unequal variances, two-sided significance level of 0.05 and a power of 90%. Accordingly, the required sample size for this arm is 68 per group. To allow for potential loss to follow-up and to address the main secondary endpoints, we include a sample size of 85 per group in this arm of the trial: 85 in the HCL control treatment group and 85 in the DHFCL index treatment group.

3.2 Study arm 2: MDI+FGM/CGM as control treatment and DHFCL as index treatment.

Previous studies showed a mean TIR under MDI+FGM/CGM treatment of 50-59% (SD of 12 to 20%).⁵ To be conservative again, we assume a mean TIR in the MDI+FGM/CGM control group of 70% (SD 20%) and for the DHFCL index intervention of 85% (SD 4%) (similarly as above), thus assuming a 15% increase in mean TIR due to the index intervention. Using the two sample t-test with unequal variances, two-sided significance level of 0.05 and a power of 90%, the required sample size for this arm is 22 per group. To allow for potential loss to follow-up and to address the main secondary endpoints we include a sample size of 35 per group in this arm of the trial: 35 in the MDI+FGM/CGM control treatment group and 35 in the DHFCL index treatment group.

4. Outcome measures

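### The primary mixed model lets residual variance differ by visit but not by treatment group, although both arms are sized on SDs of 4% versus 17% or 20%

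*SAP*

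**What the plan says.** Sections 3.1 and 3.2 plan for very different spreads in the two treatment groups. Arm 1 assumes 78% (SD 17%) on HCL against "85% under the index intervention treatment (SD 4%), using the two sample t-test with unequal variances". Arm 2 assumes 70% (SD 20%) on MDI against the same 85% (SD 4%). The results are that "the required sample size for this arm is 68 per group" in arm 1 and "the required sample size for this arm is 22 per group" in arm 2, raised to 85 and 35 per group for enrolment.

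Section 6.1 fits one linear mixed model per arm to the four follow-up visits, with a random centre intercept and a "heterogeneous autoregressive matrix that assumes different variances for each measurement". No treatment-specific matrix is named. Changing the matrix is provided for only when the model fails to converge.

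The same section lists normality and homoscedasticity as assumptions to be judged from plots of Cholesky-transformed residuals. It gives two remedies. "Violation of the assumption of homoscedasticity will be corrected with robust" (Huber-White type) standard errors. A serious departure from normality changes the main analysis to a mixed beta regression with a random intercept and no residual covariance matrix.

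**The concern.** The design assumes a variance ratio of 17²/4² = 18 in arm 1 and 20²/4² = 25 in arm 2. The primary model starts from a ratio of 1. When the numbers observed at 12 months differ between groups, a common variance gives the wrong standard error for the 12-month contrast: too small if the more variable control group is the smaller one, too large if the DHFCL group is.

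Both remedies are chosen after the data of an open-label trial have been inspected, although the inequality was assumed at the design stage. The choice decides which p-value is compared with 0.05. One of the two remedies replaces the model altogether, and the unequal variances can set it off even when each group is perfectly normal.

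**Working it through.** **Inputs.** From sections 3.1 and 3.2: SD 4% v 17% and 4% v 20%, differences of 7 and 15 points, two-sided 0.05, 90% power, 85 and 35 enrolled per group. Assumed, because the SAP gives no retention figure: a 20% loss in one group only (85 to 68; 35 to 28), other retention patterns of 70-95%, and within-patient correlations of 0.5 and 0.8.

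**Step 1, the plan's own figures.** Power of the unequal-variance t-test (noncentral t, Satterthwaite degrees of freedom) first reaches 90% at 68 per group in arm 1 (90.4%) and 22 in arm 2 (91.0%). Both stated sizes are reproduced, so these SDs are the design basis.

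**Step 2, standard error at 12 months.** True SE = √(s₁²/n₁ + s₂²/n₂). Common-variance SE = √[s_p²(1/n₁ + 1/n₂)], with s_p² = [(n₁−1)s₁² + (n₂−1)s₂²]/(n₁+n₂−2).

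Worked case, arm 1 with 85 DHFCL and 68 HCL: s_p² = (84×16 + 67×289)/151 = 137.1; common SE = √[137.1×(1/85 + 1/68)] = 1.905; true SE = √(16/85 + 289/68) = 2.107; ratio 0.904.

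| Arm | DHFCL / control | Common SE | True SE | Common SE is | Simulated type I error |
|---|---|---|---|---|---|
| 1 | 85 / 85 | 1.894 | 1.894 | correct | about 5% |
| 1 | 85 / 68 | 1.905 | 2.107 | 10% too small | about 8% |
| 1 | 68 / 85 | 2.108 | 1.907 | 11% too large | about 3% |
| 2 | 35 / 35 | 3.448 | 3.448 | correct | about 5% |
| 2 | 35 / 28 | 3.458 | 3.840 | 10% too small | about 8% |
| 2 | 28 / 35 | 3.845 | 3.464 | 11% too large | about 3% |

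With group-specific variances (Welch) the simulated error was 4.9-5.1% in every case of the main simulation.

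**Step 3, all four visits.** Earlier visits of patients who drop out recover some information. This was a large-sample calculation with one covariance matrix for both groups and dropout completely at random. Retention of 95% DHFCL / 80% control gives a type I error of 6.3-6.8%, against 7.2-7.4% on 12-month data alone. The reverse, 80% / 95%, gives 3.5-3.9%. A 10-point gap (90% / 80% or the reverse) moves the SE by about 4-5%, giving 5.8-6.2% or 3.9-4.2%.

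**Step 4, with the planned robust SE.** At 12 months, without a small-sample correction, type I error is about 5.3% in arm 1. In arm 2 it is 5.7-5.9% with t critical values and 6.1-6.4% with normal ones.

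**Step 5, the normality check.** Pool two normal residual distributions in equal numbers. Kurtosis = [3(s₁⁴ + s₂⁴)/2] / [(s₁² + s₂²)/2]².

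- Arm 1: [3(256 + 83,521)/2] / 152.5² = 125,665.5 / 23,256.25 = 5.4.
- Arm 2: [3(256 + 160,000)/2] / 208² = 240,384 / 43,264 = 5.6.

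A normal distribution has 3. As a stand-in for reading a QQ-plot, the Shapiro-Wilk test rejected normality in about 100% of simulated arm 1 trials (85/85) and 97% of arm 2 trials (35/35), against 5% after standardising within group. The Cholesky transformation uses the same pooled matrix, so it does not remove the mixture.

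**Step 6, where that switch leads.** Beta-distributed data with the planned means and SDs were fitted with a single precision for both groups. In a single-visit fit the 7-point difference of arm 1 became about 1.4 points. In a random-intercept fit (correlation 0.5 and 0.8) it became 2.2-3.1 points, and the 15 points of arm 2 became about 11. With both true means at 80% (SD 4% v 17%) the random-intercept fit showed a spurious difference of about −4.6 points. This is bias in the estimate, and it arises with complete follow-up.

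**The case against.** A reader might infer that the confidence interval and p-value are wrong whenever retention differs. The SAP does not support that. Section 6.1 commits to robust standard errors once homoscedasticity is seen to fail, and Step 4 shows that they bring the error close to nominal in arm 1 and mildly above it in arm 2. In the first analysis the fixed effects are only time, treatment and their interaction, so predicted values separate largely by group, and a four- to fivefold SD ratio should be visible in the prescribed plot.

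The retention gaps are assumptions. The one differential loss the SAP foresees, withdrawal because DHFCL is not tolerated (section 7.3), makes the common-variance test conservative. Patients who stop DHFCL but stay in the study are still measured. The planned SDs are also not known residual SDs: DHFCL discontinuers may widen their group, and adjustment for baseline TIR in the second analysis may narrow the controls.

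All of this stands, and it limits the size of the problem. Three things remain. The trigger is a visual judgement without a threshold, for an inequality the plan already assumes. No small-sample correction is named for a robust SE with 35 per group. And the robust SE does not address the normality route. The SAP does require a serious violation before switching, and Step 5 shows that the switch can be triggered, not that it will be. Section 6.1 also names no treatment-specific dispersion for the beta model; Step 6 applies if it is fitted with a common one.

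**Conclusion.** The point holds in a limited form. Read in the ordinary way, the initial primary model leaves out a between-group variance difference on which the sample size depends. Unless the robust-SE fallback is triggered, an assumed one-sided loss of 20% puts the 12-month standard error about 10% too low or 11% too high; smaller gaps and the use of all four visits reduce this, and equal numbers remove it. It would be wrong to read this as a type I error of 8% under the plan as written, because the planned robust SE largely repairs it. The less obvious risk is the normality check, which the planned SDs alone can fail and which leads to a model that, with common precision, biases the primary estimate even without dropout. The sizes rest on the planned SDs, the assumed retention and correlations, and dropout completely at random. Robust SEs also leave the pooled matrix as the weighting for incomplete patients; that effect was not quantified.

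**What to change.** In section 6.1, state from the outset that the residual covariance matrix is estimated separately for DHFCL and control within each arm (for example a REPEATED statement with GROUP=treatment in SAS), with Satterthwaite or Kenward-Roger degrees of freedom. Carry out the residual checks after standardising within treatment group. If that model does not converge, use the pooled matrix with robust standard errors clustered on patient and a named small-sample correction. If the beta fallback is kept, let its dispersion differ by treatment group.

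The cost is a few sentences in the SAP and one model option, with no new data. The heterogeneous autoregressive matrix over four visits has four variances and one correlation, so there are five extra covariance parameters per arm. This brings somewhat more risk of non-convergence in arm 2, where there are 35 patients per group; the stated fallback covers that.

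### The primary model's autoregressive correlation is restrictive, unchecked and has no named replacement; an unstructured matrix as first choice is a cheap improvement

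*SAP*

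**What the plan says.** SAP section 6.1 takes "TIR at 3, 6, 9 and 12 months (hence forward referred to as time) as dependent variable". The model "includes a random intercept for center of inclusion and a residual covariance matrix to correct for multiple measurements per patient". So the random intercept is for centre, and no patient effect stands beside the residual matrix. On that matrix the section says: "The initial analysis will be performed with a heterogeneous autoregressive matrix that assumes different variances for each measurement", with "a constant correlation between adjacent measurements and consistently lowering correlation when time between measurements is longer". The comparison that counts is at the last visit: "a specific contrast will be included in the analysis to compare mean TIR at 12 months".

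On revising the matrix, the section says: "The primary analysis may result in convergence problems when the residual covariance matrix is not correctly specified, given the data". It continues: "In this case, the residual covariance matrix may be adjusted". No replacement structure or order is given. A separate rule replaces the whole model with a beta regression and a random intercept if normality is seriously violated; the residual matrix is then dropped.

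The listed residual checks cover normality, homoscedasticity and linearity. Robust standard errors are reserved for heteroscedasticity. The model was chosen because "it allows to incorporate all non-missing measurements of patients over time", and section 7.2 keeps imputed outcomes out of the primary analysis.

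**The concern.** With no patient effect in the model, a single correlation parameter carries all dependence between a patient's visits. Section 6.1 treats a wrong matrix as something that shows itself through non-convergence. A five-parameter matrix can converge without trouble and still describe the correlation badly, and none of the planned checks would reveal it.

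With complete data this hardly matters. With incomplete data, the matrix decides how a patient's earlier visits inform the missing 12-month value. Under a first-order autoregressive rule only the last observed visit counts, and its influence fades quickly with distance. If patients have a stable TIR level, that rule under-corrects for dropout that depends on earlier TIR. At stake is the 12-month contrast, the only comparison for which the SAP reports a p-value. Leaving the replacement open also means that the matrix could be chosen after the data are seen.

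**Working it through.** **1. The plan's own figures.** Section 3 gives 68 per group (78% vs 85%, SDs 17 and 4) and 22 per group (70% vs 85%, SDs 20 and 4), for a t-test with unequal variances, two-sided 0.05 and 90% power. Both reproduce: power is 90.4% at 68 and 91.0% at 22. Enrolling 85 and 35 leaves room for losing 1 − 68/85 = 20% and 1 − 22/35 = 37%. The SAP states no within-patient correlation, dropout rate or dropout mechanism, so those below are assumptions.

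**2. What the matrix imposes.** Parameters: 4 variances + 1 correlation = 5; unstructured has 4 × 5 / 2 = 10. The autoregressive rule is corr(visit j, visit k) = ρ^|j−k|, so months 3 and 12 have ρ³. With ρ = 0.7 this is 0.34. If the true correlation is flat at 0.7, a patient 10 points below the group mean at month 3 and missing afterwards should be expected 0.7 × 10 = 7.0 points below it at month 12 (equal variances). The model implies 0.343 × 10 = 3.4 points.

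**3. Large-sample bias.** Maximum likelihood fits on 400,000 simulated patients per group, with group-by-visit means, one matrix shared by both groups, and no centre effect or baseline covariate. Dropout is monotone. Where it depends on TIR (MAR), the logit hazard changes by 1 per SD of the last observed value, with low TIR leaving unless stated. Bias is in TIR points for DHFCL minus control; simulation noise is about 0.03.

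| True correlation | SDs (index, control) | Dropout | Autoregressive | Unstructured |
|---|---|---|---|---|
| any tested | 12, 12 or 4, 17 | 20%, completely at random | about 0 | about 0 |
| AR(1), 0.7 | 12, 12 or 4, 17 | 20% MAR | about 0 | about 0 |
| flat or slowly decaying | equal | 20% MAR, alike in both | about 0 | about 0 |
| flat 0.7 | 12, 12 | 10% MAR, index only | +0.22 | 0.00 |
| flat 0.5–0.7 | 12, 12 | 20% MAR, index only | +0.46 to +0.52 | 0.01 to 0.03 |
| flat 0.5–0.7 | 12, 12 | 20% MAR, opposite directions | +0.92 to +0.99 | about 0 |
| flat 0.5–0.7 | 4, 17 | 20% MAR, both | −0.49 to −0.54 | 0.00 |
| flat 0.5–0.7 | 4, 17 | 20% MAR, index only | +0.14 to +0.15 | within 0.02 |

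A slowly decaying correlation (patient effect plus autoregression) gave autoregressive biases of 0.10 to 0.58 in size under differential or unequal-SD dropout, and about 0 for unstructured.

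**4. Scale.** Complete-data SE, arm 1: √((17² + 4²)/85) = √(305/85) = 1.89. A bias of 0.5 is 0.5/1.89 = 0.26 SE (95% CI coverage 94.2%) and 7% of the assumed 7 points. A bias of 1.0 is 0.53 SE (91.8%) and 14%. Arm 2: √((20² + 4²)/35) = 3.45; coverage is 94.8% and 94.0%.

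**5. Trial-size samples.** 200 replicates, flat 0.7, 20% dropout, MAR in the index group only.
- 85 per group, SD 12: mean bias +0.38 autoregressive, −0.03 unstructured; SD of the estimate 2.13 and 2.07.
- 35 per group, SD 12: +0.56 and +0.09; SD 2.90 and 2.94.
- 85 per group, SDs 4 and 17: +0.47 and +0.32, with simulation error of about 1.94/√200 = 0.14. The difference of 0.15 agrees with step 3.

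The unstructured fit was finite in every replicate.

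**6. Where unstructured is not clean.** With flat correlation of 0.3 in index and 0.7 in control, one shared unstructured matrix was biased by −0.20 to −0.68 (autoregressive: −0.94 to 0.00).

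**The case against.** Heterogeneous autoregressive is a recognised structure and it is prespecified. Three stronger readings are tempting, and the SAP supports none of them.

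- *A reader might infer that ordinary dropout biases the primary result.* It needs three things together: dropout that depends on TIR, a true correlation that departs from the autoregressive pattern, and effects that do not cancel between groups. The SAP gives no figure from which any of these could be established. A stable patient level in TIR is plausible but is not shown.
- *A reader might infer that an unstructured matrix removes the problem.* Step 6 shows otherwise when correlation differs by group. Baseline adjustment adds a further limit: with baseline TIR entered as a single slope, unstructured was itself off, in some settings by up to about 1 point and by more than the autoregressive model. Baseline-by-visit terms removed this when SDs were equal. No matrix cures dropout that depends on unobserved TIR.
- *A reader might infer that non-convergence is the only way the matrix can change.* The beta-model switch is a second route, and a plausible one for a bounded outcome with an assumed mean of 85%. It is triggered by non-normality, however, and not by a poor correlation fit.

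The second analysis in section 6.1 adjusts for baseline TIR, which absorbs part of the stable patient level. With flat correlation 0.7 and 20% MAR dropout in both groups, adjustment took the autoregressive bias from −0.49 to −0.24 (SDs 4 and 17). With baseline SD 17 in both groups, follow-up SDs 4 and 17 and about 25% dropout, it did not help: −0.9 to −1.2, against −0.2 to −0.4 for unstructured. So adjustment reduces the concern in some settings and does not remove it.

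Sections 7.3.1 and 7.3.2 plan wide-format imputation by treatment group, which does not impose autoregressive decay. That is partial cover. The first is run only if more than 6 (arm 1) or 3 (arm 2) patients withdraw for intolerability, and the second addresses a hypothetical full-adherence question. Neither is a refit of the primary model with another matrix.

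**Conclusion.** The point holds as a conditional risk. The first-choice matrix is restrictive, its correlation pattern is not checked, and its replacement is unnamed. Under 10–20% TIR-dependent dropout that differs by group (or with unequal SDs) and a flat or slowly decaying correlation, the 12-month difference can be off by roughly 0.1 to 1 point, about 1% to 14% of the effect assumed in arm 1. Some harsher settings went slightly above 1.

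The direction is not fixed. With the SAP's SDs of 17 and 4 and low-TIR dropout among controls, the bias shrinks the DHFCL benefit (0.4 to 0.7 points with 22% of controls missing at 12 months). With such dropout in the index group only, it enlarges the benefit slightly.

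This does not threaten the trial's main conclusion at the assumed effects of 7 and 15 points. It is a cheap improvement, because unstructured was no less precise in any material way and is feasible for four visits and 70 to 170 patients.

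**What to change.** Amend section 6.1 before outcome data are examined by group:

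- Make an unstructured residual matrix for the four visits the first choice, with a small-sample degrees-of-freedom correction such as Kenward-Roger.
- Name an ordered list of simpler structures, used only on non-convergence, with robust standard errors for them. The order is a matter of judgement. One that fits the concern is heterogeneous Toeplitz, then heterogeneous compound symmetry, then heterogeneous autoregressive. Robust standard errors protect the interval width; they do not remove bias in the estimate.
- In the adjusted model, let baseline TIR interact with visit.
- Add group-specific covariance matrices as a sensitivity analysis, since section 3 assumes SDs of 4 against 17 or 20.

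Section 6.2 applies the primary specification to continuous secondary outcomes, so the wording would carry over. The cost is a SAP edit, 10 − 5 = 5 more covariance parameters, a few baseline-by-visit terms, and negligible loss of precision.

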6.2 Secondary endpoints

The analysis for continuous secondary outcomes follows the analysis specifications of the primary outcome (see above), except when distributional assumptions are not met. In this case, a log-transformation will first be used and subsequently assessed with residual analyses. When log-transformations still show deviations from distributional assumptions, alternative distributions or non-parametric analysis will be considered. As for the analysis of the primary outcome, all regression analyses will be performed by adjusting for the same a priori defined prognostic factors and repeated measurements.

Binary secondary outcomes will be analyzed with mixed logistic regression analysis. Secondary count outcomes (e.g. the number of hypoglycemic events) will be analyzed with a generalized linear mixed model: the distributions utilized will depend on the observed distribution. Initial analysis will be performed with a negative binomial distribution. The distribution may show a high number of patients with zero events. If so, the distribution will be adjusted to either a zero-inflated Poisson distribution or a zero-inflated negative binomial distribution.²⁰ For binary and count outcomes, analyses with a random intercept will initially be performed, as these analyses may be performed under maximum likelihood estimation. Assumption for linearity will be assessed and adjustments will be made when necessary.

Secondary outcomes measured only once during follow-up (i.e. at 12 months) will be analyzed with linear, logistic and negative binomial regression models (as applicable) without adjustment for repeated measurements (i.e. regular linear and logistic regression). Results from linear models will be reported as a difference in means (with 95% Cls). For binary outcomes, results will be reported as odds ratios with 95% Cls. For negative binomial models for count outcomes, results will be reported as rate ratios with 95% Cls.

Secondary endpoints will be considered supportive and are not included in the formal testing strategy. P-values will therefore not be provided.

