7.3.2 Intolerability and continuation of study measurements

Intolerability of the DHFCL is also of concern for patients who discontinue treatment while continuing with the study. Follow-up measurements in these patients will be performed as planned, and these measurements will be included in the ITT analysis as described in section 6.1. The treatment effect derived from the ITT analysis, while being of primary interest for decision making, will not represent the full treatment potential of the DHFCL. Results of the PP analysis may be biased, as balance between treatment groups after randomisation may be lost. To further evaluate the beneficial effect of the DHFCL, two additional sensitivity analyses will be performed.

The first analysis aims to evaluate the treatment effect under a hypothetical scenario where all patients were treated with the DHFCL and were fully adherent. Initially, observations of the outcome after treatment discontinuation or non-adherence will be excluded from the analysis and set to missing. Subsequently, multiple imputation will be used to impute these outcomes. Multiple imputation will be applied as described in section 7.1, inclusion of additional variables in the imputation model will be considered based on clinical literature as well as observed patterns of missing data and discontinuation. As described in section 7.1, imputations will be performed for each arm and each treatment group separately. Analysis of the primary outcome will be performed as described in section 6.1. In an additional step, all follow-up outcomes, both prior to or after discontinuation or non-adherence, will be set to missing and imputed. Again, the resulting imputed data will be analysed as described in section 6.1. It should be noted that imputations described in this section will be performed separately from imputations described in sections 7.1.

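### Section 6.1 plans an unadjusted and an adjusted model but one p-value per arm, and the SAP's rules for patients without a valid baseline TIR conflict

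*SAP*

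**What the plan says.** **The model.** SAP section 6.1 describes two fits of the longitudinal model. For the unadjusted one: "The first analysis will include time, treatment and an interaction between time and treatment as fixed effects". For the adjusted one: "In the second analysis, correction for the predefined prognostic factors, i.e. TIR at baseline, patients age and sex, will be included". On testing it says "P-values will only be reported for the primary analysis in the ITT population", and then "The p-value for study arm 1 and study arm 2 will each be separately compared to the threshold 0.05 to declare significance".

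The label of primary analysis is attached to something both fits share: "The regression model with residual covariance matrix is specifically chosen as the primary analysis". The beta-regression fallback in the same section carries both covariate steps forward. Section 6.2 describes the primary outcome as adjusted: "As for the analysis of the primary outcome, all regression analyses will be performed by adjusting for the same a priori defined prognostic factors". Section 7.3.2 refers back to 6.1 as though it held one analysis: "Analysis of the primary outcome will be performed as described in section 6.1".

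**The analysis set.**
- Section 5 puts all randomised participants in the ITT analysis.
- Section 5.1 admits to the primary analysis those with at least 168 hours of blinded sensor data both at baseline and at one or more follow-up visits. It also sets a baseline with fewer hours to missing.
- Section 7.1 multiply imputes missing baseline variables, and the primary outcome at baseline is among the variables imputed.
- Section 7.2 includes patients on the strength of valid follow-up data. It allows exclusion for an incomplete baseline only when the patient leaves before month 3.

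**The concern.** Each arm has one confirmatory test, so the plan should lead any two analysts to the same p-value. Here it does not. If the two models fall on opposite sides of 0.05, section 6.1, where the test is defined, has no rule for which one counts. One reader may take the first-listed analysis as primary; another may follow 6.2 and take the adjusted one.

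The second problem concerns who is analysed. Followed literally, 5.1 drops a randomised patient with a short baseline recording even when follow-up TIR is valid and 7.1 would impute the baseline value. That gives up precision, departs from the ITT statement in section 5, and leaves imputed baseline TIR with no use in the primary model.

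**Working it through.** **1. The plan's own figures.** Inputs from SAP 3.1 and 3.2: arm 1, 7 points, SDs 17 and 4; arm 2, 15 points, SDs 20 and 4; two-sided 0.05, 90% power, unequal-variance t-test. With SE = √[(SD₁² + SD₂²)/n]:
- Arm 1, n = 68: SE = √(305/68) = 2.118, effect/SE = 3.31, power 90.4%.
- Arm 2, n = 22: SE = √(416/22) = 4.348, effect/SE = 3.45, power 91.0%.

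These are the smallest n reaching 90%, so the stated 68 and 22 reproduce. At the enrolled sizes:
- Arm 1, n = 85: SE = √(305/85) = 1.894, df = 84 × 305²/(289² + 16²) = 93.3, power 95.5%.
- Arm 2, n = 35: SE = √(416/35) = 3.448, power 98.9%.

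**2. How far apart the models can be.** The SAP gives no correlation between baseline and follow-up TIR, so 0.3 to 0.7 is assumed, with adjacent-visit correlation 0.7 to 0.85. A simulation of months 3, 6, 9 and 12 used the plan's SDs, baseline SD equal to control SD, a saturated time-by-treatment model with working AR(1), patient-cluster robust SEs, and 8,000 runs per cell. Loss, where assumed, was 5/10/15/20% at the four visits, at random.

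| Planned effect | Arm 1 power, unadjusted / adjusted | Arm 1 disagree | Arm 2 power, unadjusted / adjusted | Arm 2 disagree |
|---|---|---|---|---|
| No loss | 95–96% / 96–99.6% | 2–4% | 99% / 99–100% | about 1% |
| 20% loss by month 12 | 92–93% / 93–98.5% | 3–7% | 97–97.5% / 97.5–99.7% | 1–3% |

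The arm 1 95% CI half-width without loss is 3.75 points unadjusted and 3.03 to 3.64 adjusted.

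At half the planned effect (3.5 and 7.5 points; no loss; adjacent-visit correlation 0.7), disagreement for correlations 0.3/0.5/0.7 is 8.6/15.2/25.0% in arm 1 and 7.7/14.8/21.9% in arm 2. Arm 1 power there is 44–46% unadjusted and 47.5–62.1% adjusted.

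**3. Under the null.** Each test alone holds its level (4.2–5.2% in 12,000 runs per cell). For a single 12-month outcome with equal variances, the two z statistics have correlation √(1 − ρ²) = 0.954, 0.866, 0.714 for ρ = 0.3, 0.5, 0.7. The chance that at least one rejects is then 6.4%, 7.3%, 8.3%. The four-visit simulation gives 6.0–8.2% (arm 1) and 5.9–7.5% (arm 2). These figures apply only if either model were allowed to decide, which the SAP does not say.

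**4. The baseline rule.** Take a patient with under 168 hours at baseline and a valid month-12 TIR. Section 5 includes this patient and the opening rule of 5.1 excludes them. The set-to-missing rule in 5.1, read with 7.1, supplies an imputed baseline. Section 7.2 includes them on the follow-up data. These rules cannot all hold.

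The SAP gives no rate of short baselines. Assuming 5/10/15%, arm 1 keeps 85 × 0.95, 0.90, 0.85, about 81/76/72 per group. With the 20% loss, adjusted power (6,000 runs) falls from 93.1% to 91.8/90.0/88.2% at correlation 0.3, and from 98.4% to 97.9/96.4/95.6% at 0.7. The comparison treats an imputed baseline as if observed, so these losses are upper bounds.

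**The case against.** The strongest reply is that the SAP already leans to the adjusted model. Section 6.2 says outright that the primary outcome is analysed with adjustment. Section 7.2, by barring imputed outcomes from the primary analysis while allowing baseline imputation, implies that imputed baseline values enter it, and the unadjusted model has no baseline covariate. This stands as evidence of intent, and it is why the fix names the adjusted model. It is not a designation: 6.2 governs endpoints that receive no p-values, and 6.1 lists the unadjusted model first.

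On the analysis set, it can be said that only the opening rule of 5.1 points to exclusion, and that 7.1 keeps a use elsewhere, for example in the propensity model of 7.3.2. Both are true. But 5.1 is the section that defines who enters the primary analysis, so an analyst would follow it, against section 5.

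On size, disagreement is rare at the planned effect and the larger figures need a smaller true effect. That stands. The simulation also uses a working AR(1) with robust SEs rather than the planned heterogeneous autoregressive matrix with a centre intercept, so its figures are illustrative.

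A last caution is that 7.1 imputes by group with all outcomes in wide format: some 13 glycaemic measures at five visits make 65 variables for 35 patients per group in arm 2. This deserves attention, but 7.1 already plans it; the fix does not create it.

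**Conclusion.** Both parts hold. Section 6.1 has two models, one decision p-value per arm and no sentence joining them; the hints elsewhere favour the adjusted model but do not settle it. Section 5.1 as written contradicts section 5, its own set-to-missing rule, and sections 7.1 and 7.2.

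The consequence is modest if the planning assumptions are right and material if the true effect is nearer half of what was planned. The sizes rest on assumed correlations, loss and rates of short baseline recordings. Centre, age, sex, an estimated covariance matrix and multiple imputation were not modelled. The textual conflict does not depend on any of these. The trial is not invalidated, but the decision rule and the primary population should be fixed before database lock.

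**What to change.** **Section 6.1.** State that in each arm the model with baseline TIR, age and sex is the single primary analysis, and that its 12-month contrast supplies the estimate, the 95% CI and the p-value compared with 0.05. State that the unadjusted model is supportive, with estimate and CI only, and that the same designation applies if the beta-regression fallback is used.

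**Section 5.1.** Remove the valid-baseline condition. Every randomised patient with at least one valid follow-up TIR enters the primary model as randomised; a baseline TIR from under 168 hours is set to missing and imputed under 7.1.

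**Section 5.** Align the ITT sentence: the primary ITT set is all randomised patients with at least one valid follow-up TIR, with the number lacking one reported per group; safety analyses include all randomised patients. Section 7.2 can stand, since patients who leave before month 3 have no follow-up TIR and fall outside this set anyway.

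**Cost.** Wording only: three sentences in 6.1, the inclusion rule in 5.1 and one sentence in section 5. No new data are needed and both models are kept. The downside is that the primary result relies on imputed baseline TIR for the patients who lack it.
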